8.2.1 Anticipated Adverse Effects

The following adverse effects could occur in association with insertion, removal, and/or use of the Senseonics CGM System Sensor and/or Transmitter:

- Infection, local or systemic, possibly resulting in sensor removal
- Excessive bleeding during insertion or removal
- Bruising or swelling
- Poor wound healing after insertion or removal
- Keloid and/or scar formation
- Excessive or prolonged pain or discomfort at the Sensor site
- Nerve damage causing tingling, numbness, pain or weakness
- Uncomfortable heating
- Burn
- Electrostatic shock
- Skin irritation and/or redness
- Itch
- Discoloration of skin
- Hematoma formation
- Device migration
- Skin erosion
- Allergic reaction to the device components, local anesthetic, or other medication or materials used in the procedure
- Anxiety and/or nervousness and/or lack of sleep
- Device fragments or particulate matter remaining in the body
- Failure to retrieve device or device left behind
- Difficulty in removing device that may require surgery
- Device malfunctions of the Sensor and/or Transmitter with possible need to remove and/or replace the Sensor and/or Transmitter
- Burning sensation or pain.
- Elevated blood pressure
- Water retention in the tissue, swelling or edema
- Airway spasms

- Shortness of breath
- Circulatory disorders
- Confusion
- Disorientation
- Increased or decreased sensitivity to touch or pain
- Metallic taste
- Sleepiness
- Visual disturbances and/or blurred vision
- Tinnitus
- It is possible that the local anesthetic could cause a reaction other than listed or previously seen.
- Fluid/electrolyte disturbances such as fluid retention
- Muscle weakness
- Osteoporosis
- Peptic ulcer
- Pancreatitis
- Ulcerative esophagitis
- Impaired wound healing
- Headache
- Psychic disturbances and mood swings
- Convulsions
- Glaucoma
- Weight gain
- Nausea and/or vomiting
- Malaise
- Irritability
- Insomnia
- Heartburn
- Hyperglycemia
- Ketosis
- Headaches
- Dizziness, lightheadedness, and/or fainting
- It is possible that the use of the Senseonics CGM system could cause a reaction other than listed or previously seen.
- It has not been determined whether the risks usually associated with injectable dexamethasone apply to the use of dexamethasone elution ring, a highly localized, controlled-release device.
- The dexamethasone ring could cause other adverse events not listed or previously seen.

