8.2.3 Risks Associated with Participation in the Clinical Investigation

This clinical investigation involves subjects with diabetes mellitus. These subjects may experience hyperglycemia and hypoglycemia as a consequence of their existing condition and medical management (e.g. insulin administration). For this study, hyperglycemia and hypoglycemia will not be reported as adverse events unless meeting criteria of a Serious Adverse Event. Episodes of hyperglycemia and hypoglycemia as documented by the Subject SMBG Meter will be reported in an extra listing separate from the AE listings. Should a known side effect(s) occur to administered medication(s) used in the intervention, such effects will be reported as part of the adverse event description and will not be considered a separate adverse event.

The amount of blood drawn for in-clinic testing during the study is below the acceptable limits of blood donation of approximately 475 mL; hence it does not pose any additional unacceptable risk to the subjects.

This clinical investigation involves the following procedures that present risk: placement of an intravenous catheter, frequent blood sampling, and conduct of hyperglycemia and hypoglycemia challenges at the clinic visits. In addition, Subjects in this study may use an insulin pump or syringes to administer subcutaneous insulin.

The following risks are potentially associated with such procedures:

- Routine administration of insulin may cause hematoma, redness, swelling and itch at the injection site, skin rash, itch, sweating, gastro-intestinal complaints, edema, difficulty breathing, palpitations and drop in blood pressure, and even death.
- Hypoglycemic symptoms requiring medical intervention which may include seizures, neuroglycopenia, coma and even death (including occurrence during home use)
- Insulin administration leading to hypoglycemia include: cold sweating, cool and pale skin, fatigue, nervousness, shakiness, anxiety, weakness, confusion, feeling of numbness, hunger, impairment of vision, problems with concentration, headache, nausea, palpitations, coma, or death.

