9.1 Adverse Event Definitions

Adverse Event (AE) is defined as any untoward medical occurrence, unintended disease or injury, or untoward clinical signs (including abnormal laboratory findings) in subjects, users or other persons, whether or not related to the investigational medical device.

NOTE 1 This definition includes events related to the investigational medical device or the comparator.

NOTE 2 This definition includes events related to the procedures involved.

NOTE 3 For users or other persons, this definition is restricted to events related to investigational medical devices.

Serious Adverse Event (SAE) is defined as an adverse event that:

- Leads to death;
- Leads to a serious deterioration in the health of the Subject that either:
 - Results in life-threatening illness or injury; or
 - Results in a permanent impairment of a body structure or a body function; or
 - Requires inpatient or prolonged hospitalization; or
 - Results in medical or surgical intervention to prevent life-threatening illness or injury or permanent impairment to a body structure or a body function;
- Led to fetal distress, fetal death or congenital abnormality or birth defect;
- Significant medical event.

NOTE: Planned hospitalization for a pre-existing condition, or a procedure required by the CIP, without serious deterioration in health, is not considered a serious adverse event.

Anticipated adverse events are AEs that have been identified as possible adverse events related to the investigational device or procedure.

Unanticipated adverse device effects (UADEs) are defined as any serious adverse effect on health or safety or any life-threatening problem or death caused by, or associated with, a device, if that effect, problem, or death was not previously identified in nature, severity, or degree of incidence in the investigational plan or application (including a supplementary plan or application), or any other unanticipated serious problem associated with a device that relates to the rights, safety, or welfare of study subjects.

Severity

Mild: Awareness of a sign or symptom that does not interfere with the Subject's usual activity or is transient, resolves without treatment and with no sequelae

Moderate: Interferes with the Subject's usual activity and/or requires symptomatic treatment

Severe: Symptom(s) causing severe discomfort and significant impact on the Subject's usual activities and/or requires treatment

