9.3.3 Protocol-Specific Reporting Information

For the purpose of this protocol, mild (i.e., clinically non-significant) hypoglycemia and hyperglycemia symptoms or blood glucose values out of the normal range will not be reported as adverse events unless determined to meet the criteria of a Serious Adverse Event.

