11.2 Safety Endpoints

The safety endpoint is the incidence of device-related or insertion/removal procedure-related serious adverse events (SAEs) in the clinic and during home use through 90 days post-insertion.

An Adverse Event is considered 'related' if the relatedness is categorized as 'possibly related', or 'related'. The assessment of seriousness and relatedness made by the Medical Monitor will be used for analysis. The numbers of SAEs and the percentage of patients with SAEs will be reported for each SAE type that is observed, identified as device-related, procedure-related or unrelated to the study (Table 3 in APPENDIX 1). The count and proportion of patients experiencing at least one device-related or procedure-related SAE will be presented. No inferential statistical analysis will be performed.

Other safety endpoints include:

- Incidence of insertion/removal procedure or device-related adverse events in the clinic and during home use.
- Incidence of all adverse events in the clinic and during home use.
- Incidence of hospitalizations due to hypoglycemia, hyperglycemia or ketoacidosis occurring during home use.
- Incidence of reported hypoglycemic and hyperglycemic events occurring during home use.

For each of the adverse event (AE or SAE) categories above, the numbers of AEs and the percentage of patients with AEs will be reported for each AE type that is observed and be stratified by the target age enrollment categories (Tables 4A-4E in APPENDIX 1). A listing (Table 5 in APPENDIX 1) will be prepared that identifies each patient with a reported AE or SAE, and relevant information including date of onset, severity level, seriousness, relatedness to the device or procedure, classification as anticipated or unanticipated, corrective action(s) taken, and resolution status (resolved or ongoing).

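### Section 8.2.3 bars known medication side effects from being separate adverse events, with no exception for serious ones and no list of the drugs covered, so the adverse event tables can undercount

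*Protocol*

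**What the plan says.** The rule is in Protocol Section 8.2.3, in a paragraph about hypo- and hyperglycemia. It begins "Should a known side effect(s) occur to administered medication(s) used in the intervention" and continues "such effects will be reported as part of the adverse event description and will not be considered a separate adverse event". Neither the intervention nor the medications are defined.

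Earlier in the same paragraph the protocol says that "hyperglycemia and hypoglycemia will not be reported as adverse events unless meeting criteria of a Serious Adverse Event". Section 9.3.3 has a similar exclusion, limited to mild, clinically non-significant symptoms and glucose values outside the normal range; these "will not be reported as adverse events unless determined to meet the criteria of a Serious Adverse Event". It does not mention medication side effects.

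The general rules are wider. Section 9.1 reads: "Adverse Event (AE) is defined as any untoward medical occurrence, unintended disease or injury, or untoward clinical signs". It adds: "NOTE 2 This definition includes events related to the procedures involved". Section 9.3 requires all adverse events (AEs) to be reported, and all serious adverse events (SAEs) to reach the sponsor within 48 hours. Section 8.2.1 lists, among the anticipated effects of insertion, removal or use, "Allergic reaction to the device components, local anesthetic, or other medication or materials used in the procedure".

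The main safety endpoint (Protocol 11.2; SAP 4.2.2 and 6.8) is the incidence of device-related or insertion/removal-related SAEs. Other endpoints include "Incidence of all adverse events in the clinic and during home use". Results are reported as numbers of events and percentages of patients for each AE type (Tables 3 and 4A-4E), with a listing of each event's severity, seriousness and relatedness (Table 5). The SAP neither repeats nor limits the medication rule.

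**The concern.** Sections 9.1 and 9.3 make a drug side effect an AE. Section 8.2.3 says it is not one in its own right. No text says which prevails, so up to four sites could record the same event differently.

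The rule assumes that an AE description exists into which the side effect can be written. For drugs given in a glucose challenge or as rescue, the event being treated is usually non-serious hypo- or hyperglycemia, which Section 8.2.3 does not count as an AE. The side effect may then have nowhere to go.

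The glycemic exclusions in 8.2.3 and 9.3.3 both except serious events, but the medication sentence does not. Known effects can be serious by the protocol's own account: its list of insulin effects in Section 8.2.3 extends to breathing difficulty, a fall in blood pressure and death.

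At stake are the all-AE endpoint, the counts by AE type and, by a narrower route, the main SAE endpoint. All are descriptive, so an event that is not recorded separately is not recovered later in the analysis.

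**Working it through.** The plan states no figure on this point, so the check is mainly a comparison of texts.

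**1. Which drugs, and where an effect would count**

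| Medication | Where given | What it treats or accompanies | Is that an AE? | Endpoint for a side effect |
|---|---|---|---|---|
| Insulin | 5.12.3.1, 5.12.3.2 (challenges), 7.1.5.1 | Hyperglycemia, or induced hypoglycemia | Not unless serious (8.2.3) | All AEs |
| Glucagon, IV dextrose | 7.1.4.1 (rescue) | Hypoglycemia | Not unless serious (8.2.3) | All AEs |
| Local anesthetic | Insertion; its injection marks the start of the procedure (5.1) | The procedure itself | No | All AEs and related AEs; main SAE endpoint if serious |

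The first two rows fit the Section 9.1 causality class for other study-related procedures. They would therefore normally fall outside the main endpoint even if recorded separately.

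**2. If a parent AE exists.** The side effect goes into its description. The subject already counts in the all-AE percentage, which does not change. The number of AEs falls by one, the side effect's own type loses an event, and Table 5 has no line for its severity, seriousness and relatedness. Adjudication by the Medical Monitor (13.13) and the rule that two subjects stopped for the same AE suspend part of the study (7.3) also work on identified events.

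**3. If no parent AE exists.** Suppose a subject develops a skin rash, one of the insulin effects listed in 8.2.3, after the insulin that starts a hypoglycemia challenge. The hypoglycemia is not an AE, and the rash may not be a separate one. If the subject has no other AE, the subject is missing from the all-AE percentage as well.

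**4. Scale.** Input: 36 subjects with sensors inserted (Protocol 11.3.2.2), all assumed to be in the safety population.

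- One subject not counted: 1/36 = 2.8 percentage points.
- Exact 95% limits: 0/36 has an upper limit of 1 − 0.025^(1/36) = 9.7%; 1/36 has limits of 0.1% to 14.5%.
- Chance of at least one affected subject, 1 − (1 − p)^36, at assumed per-subject rates p:
  - p = 1%: 1 − 0.99^36 = 30%
  - p = 2%: 1 − 0.98^36 = 52%
  - p = 5%: 1 − 0.95^36 = 84%

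The rates p are assumptions that show a range; the documents give none.

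**The case against.** The strongest reply is that the sentence bars only a separate AE and so presupposes a parent. With no parent, it arguably does not apply, and Section 9.1 makes the effect an AE. Section 9.3.3, in the reporting chapter, also excludes less than 8.2.3 does, so some non-serious hypoglycemia may be an AE after all. Both readings are reasonable. Neither is written down, and the second shows that 8.2.3 and 9.3.3 themselves differ.

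On serious effects, Section 9.3 requires every SAE to be reported with no drug exception, and the analysis uses the Medical Monitor's assessment of seriousness and relatedness. This stands. Loss of a serious effect is a risk from conflicting text, not a stated rule. The anesthetic route is also the weaker one, because the sentence sits among the risks of challenges and sampling, while anesthetic reactions are listed in 8.2.1.

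Three stronger readings are tempting, but the documents do not support them:

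- **Steroid effects are lost too.** Dexamethasone elutes from the sensor ring, a device component (1.1), and 8.2.1 treats its effects as adverse events. It is not naturally an administered medication.
- **The safety endpoints are biased downward.** The documents show how undercounting could occur, not that it does.
- **The missing events can be counted from the challenges.** Two challenges at each of Visits 3-5 and one at each of Visits 6-8 give 9 per subject, or 9 × 36 = 324. That is a ceiling: Section 5.12.1 excludes subjects with gastroparesis and does not expect hypoglycemia challenges in subjects not on insulin. With no side-effect rate stated, it gives no event count.

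**Conclusion.** The conflict is real and worth correcting. Section 8.2.3 denies separate AE status to known side effects of an undefined set of medications, serious ones included, against Sections 9.1 and 9.3. Followed as written, it can undercount the all-AE endpoint and the AE counts by type. This is most likely for challenge and rescue drugs, where a parent AE may not exist.

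For the main SAE endpoint the risk is narrower. It needs a serious local-anesthetic reaction that a site or the adjudicator treats under 8.2.3 rather than 9.3. One such subject would move the result by 2.8 points, from 1/36 to 0/36.

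The conclusion rests on the sentence being applied literally, and on all 36 inserted subjects forming the denominator.

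**What to change.** Replace the medication sentence in Section 8.2.3 with wording such as:

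> An untoward effect of a medication given under this protocol (e.g. insulin, glucagon, dextrose, local anesthetic), other than hypo- or hyperglycemia that is not reportable under 8.2.3/9.3.3, is recorded as its own AE with seriousness and causality assigned under 9.1, and linked to the event for which the medication was given, if any. Any effect meeting SAE criteria is always recorded and adjudicated as its own SAE.

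The exclusion for hypo- and hyperglycemia is needed. Without it, every hypoglycemia that a challenge deliberately induces with insulin would become an AE, against 8.2.3 and 9.3.3.

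Reconcile 8.2.3 with 9.1, 9.3, 9.3.3 and SAP 6.8, including the different scope of the glycemic exclusions in 8.2.3 and 9.3.3. Count these events in Tables 3-5.

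The change affects recording only, not treatment. It costs one protocol sentence and matching text in the reporting sections and the SAP; reported AE counts may rise slightly.

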4 STUDY METHODS, PROCEDURES AND CLINIC VISITS

Each visit is described in detail in this section.

Visit Number	1	2	3	4	5	6	7	8	9
Visit Type	Screening	Sensor Insertion and Training	Accuracy Visit	Accuracy Visit	Accuracy Visit	Accuracy Visit	Accuracy Visit	Accuracy Visit and Sensor Removal	Follow-up Sensor Site Assessment
Study Day and Window		Day 0 (+0 to 30 Days after Visit 1)	Day 1 (\pm 1 Day)	Day 7 (\pm 1 Days)	Day 14 (\pm 1 Days)	Day 30 (\pm 7 Days)	Day 60 (\pm 7 Days)	Day 90 (-3/+7 days)	10 Days Following Sensor Removal (-3/+7 days)
Anticipated Length of Visit	2 Hours	2 to 6 Hours	19 Hours	18 Hours	18 Hours	14 hours	14 hours	15 hours	30 Minutes
Informed Consent Process	X								
Screening history, exam, labs to assess Inclusion/Exclusion	X								
Sensor Insertion		X							

Visit Number	1	2	3	4	5	6	7	8	9
Device Training		X							
Urine pregnancy	X	X	X	X	X	X	X	X	
IV Catheter			X	X	X	X	X	X	
Approximate length of time to collect blood Samples			16 Hours	16 Hours	16 Hours	12.5 Hours	12.5 Hours	12.5 Hours	
Dexamethasone blood draw (4.0 mL) ²	X	X	X ³	X ³	X ³	X	X	X	
HCT	X		X	X	X	X	X	X	
A1C (2.0 mL)	X					X	X	X	
Fingerstick blood glucose and ketones per protocol			X	X	X	X	X	X	
Download Transmitter and BG Meters			X	X	X	X	X	X	
Assess changes in medications and Adverse Events		X	X	X	X	X	X	X	X
Assess Sensor site			X	X	X	X	X	X	X
Hypoglycemia and Hyperglycemia Challenge			X	X	X	X ¹	X ¹	X ¹	
Sleep Assessment				X	X				
Questionnaire								X ⁴	
Sensor Removal								X	
Approximate Samples for glucose analysis			89 (13 hrs @4 per, 3 hrs @ 12 per)	89 (13 hrs @4 per), 3 hrs @ 12 per	89 (13 hrs @4 per), 3 hrs @ 12 per	59 (11.5 hrs @4 per), 1 hr @ 12 per	59 (11.5 hrs @4 per), 1 hr @ 12 per	59 (11.5 hrs @4 per), 1 hr @ 12 per	
Maximum Estimated Blood Draw Volume	6	12	97	97	97	65	65	65	Total=504

1 Only hypoglycemia challenge or hyperglycemia challenge, depending on glucose level

2 Designated subjects will have 3 samples drawn at visit 2. A subset of subjects will have daily blood samples drawn for the first 7 days of sensor wear

for dexamethasone assessment. Remaining subjects may have an additional blood sample drawn during the first 7 days TBD based on the results from the subset.

3 Subjects will have 2 blood samples drawn for dexamethasone assessment, one at the beginning of the visit, and one at the end.

4 Subjects will be asked to complete a questionnaire at the end of sensor wear period.

Visit Details

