5.9 IV/Blood Draw Guidelines

5.9.1 IV Placement/Setup

IVs for blood sampling may be placed in the arm or hand. IV Access will be maintained during the sampling portion of the study for blood sampling and for the treatment of severe hypoglycemia or hyperglycemia during the study. If an IV fails, a reasonable effort should be made to replace it.

It is advised that sites use a heating pad in order to help keep IV sampling sites patent and improve blood flow.

Sites will be advised to use a dual stopcock closed-loop or single stopcock blood-wasting technique, as long as site personnel are cognizant of the following:

- The single-stopcock technique has a lower risk of diluted samples, but sites must take care not to exceed the protocol total blood loss limit of 475 ml in any 8-week period.
- Please note that when calculating waste volume to consider the volume of saline in the system that is drawn when clearing the line. This could include the extension set (0.2 ml), stopcock (0.2 ml), and cannula (0.1 ml). Therefore a 1.5 ml “waste” draw actually contains 1.0 ml blood.

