5.9.2 Timing of blood sampling

Blood will be sampled every 5-15 minutes, dependent on the value of the previous sample according to the following ranges:

- BG \geq 325 mg/dL: every 5 minutes (+/- 2 minutes)
- BG >75 mg/dL and < 325 mg/dL: every 15 minutes (+/- 2 minutes)
- BG \leq 75 mg/dL: every 5 minutes (+/- 2 minutes)

Additional samples may be drawn for YSI glucose analysis as needed for patient safety or to recheck a suspected erroneous value (e.g. dilute sample).

In the event of loss of IV access or loss of functional YSI and need for continued subject monitoring, glucose measurements will be made on capillary whole blood using the Subject SMBG meter as needed. These values will not be included in the study data set, but will only be used for subject treatment decisions.

Samples missed due to loss of IV access or loss of functional YSI will not be considered protocol deviations.

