5.9.3 Sample volume

Approximately 1.0 ml IV blood samples will be collected (after saline is cleared from sampling apparatus) in sample containers with an appropriate anticoagulant additive (BD Microtainer K2E tubes (REF 365955) or Sarstedt Monovette with K2E (REF 06.1664.001) or similar) for analysis.

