6 CLINICAL LABORATORY EVALUATIONS AND ESTIMATED BLOOD VOLUMES

Standard clinical laboratory analysis equipment, procedures and quality control will be used for all laboratory evaluations in this clinical trial. Blood samples will be drawn at Visits 1 through 8 (or sensor removal as appropriate) for laboratory dexamethasone measurement. Additionally designated subjects across the study will have blood samples drawn for dexamethasone

measurement 3 times on the insertion date, and on each day between visits 3 and 4. Samples for hemoglobin A1C measurement will also be collected at Visit 1, 6, 7 and 8. Hematocrit will be assessed using local lab or Point of Care testing device.

Total Estimated Blood Loss

Maximum estimated blood loss over the study is 504 mL.

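### Protocol 8.2.3 puts study blood loss below about 475 mL, but the protocol's own maximum is 504 mL, that maximum omits planned draws, and the 475 mL limit is per 8 weeks

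*Protocol*

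**What the plan says.** Protocol 8.2.3 tells the reader that "The amount of blood drawn for in-clinic testing during the study is below the acceptable limits of blood donation of approximately 475 mL" and concludes from this that there is no additional unacceptable risk to subjects.

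Two other places bear directly on that sentence:

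- Section 6: "Maximum estimated blood loss over the study is 504 mL". The visit tables in Protocol Section 4 and SAP Table 1 carry the same total.
- Section 5.9.1: "sites must take care not to exceed the protocol total blood loss limit of 475 ml in any 8-week period".

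On what may be drawn:

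- Section 5.9.1 on technique: "Sites will be advised to use a dual stopcock closed-loop or single stopcock blood-wasting technique". It then gives an example of a 1.5 mL waste draw that contains 1.0 mL of blood.
- Section 5.9.2: "Additional samples may be drawn for YSI glucose analysis as needed for patient safety or to recheck a suspected erroneous value".
- Section 4.3 brings the dexamethasone subset (6 to 9 subjects) back on Days 3-6 for draws of about 4 mL each, on top of the Visit 3 and Visit 4 samples.
- Visit table, footnote 2, for everyone else: "Remaining subjects may have an additional blood sample drawn during the first 7 days TBD based on the results from the subset".
- Visit table, glucose samples at each of Visits 6-8: "59 (11.5 hrs @4 per), 1 hr @ 12 per".

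**The concern.** The statement that blood loss is acceptable rests on one number, and the protocol contradicts that number elsewhere. Section 8.2.3 also takes a limit that 5.9.1 defines over 8 weeks and applies it to a study of about 4.5 months per subject. An ethics board or site reading 8.2.3 alone would believe the whole study stays under a donation-sized volume.

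The 504 mL needs checking too, because sites and boards will treat a published maximum as a ceiling. If it leaves out planned draws, or all waste, subjects can give more than they were told. Section 8.2.3 itself lists anemia due to blood sampling as a risk.

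**Working it through.** **Inputs.** 1.0 mL per glucose sample (5.9.3). 4.0 mL per dexamethasone draw and 2.0 mL per A1C draw (visit table). Two dexamethasone draws at each of Visits 3-5 (footnote 3). At Visit 2, three draws for the subset and one for other subjects (4.2.4). Fingerstick and hematocrit volumes are not given and are not counted.

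**Reproducing 504 mL.**

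- Visit 1: 4 + 2 = 6. Visit 2: 3 × 4 = 12, which is already the subset figure.
- Visits 3-5: 13 × 4 + 3 × 12 + 1 = 89 samples; 89 + 2 × 4 = 97 mL each.
- Visits 6-8: 11.5 × 4 + 1 × 12 + 1 = 59 samples; 59 + 4 + 2 = 65 mL each.
- Total: 6 + 12 + 3 × 97 + 3 × 65 = 504 mL. This matches exactly, and it shows that no waste is included. 504 − 475 = 29 mL, or 6% of 475.

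**What 504 mL leaves out.**

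- Day 3-6 draws, every subset subject: 4 × 4 = 16 mL, so 504 + 16 = 520 mL.
- Second hour of 5-minute sampling in a hypoglycemia challenge at Visits 6-8. The 4.6 timeline targets 24 values at 5-minute intervals (2 hours), and 5.12 gives 120 minutes. Samples: 10.5 × 4 + 2 × 12 + 1 = 67, which is 8 more than 59, so 73 mL per visit. The three-hour budget at Visits 3-5 does fit one hyperglycemia hour plus two hypoglycemia hours.
- Subset with 0, 1, 2 or 3 such challenges: 520, 528, 536 or 544 mL.
- Non-subset: 504 − 8 = 496 mL, or 500 with the possible week-1 draw. With three such challenges: 496 + 24 = 520, or 524.

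**8-week totals before waste.**

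- Visits 1-6 with the hypoglycemia option at Visit 6: subset 6 + 12 + 16 + 291 + 73 = 398 mL; non-subset 6 + 4 + 291 + 73 = 374 mL. These fit in 56 days if, for example, screening is at most 26 days before insertion and Visit 6 is on Day 30.
- Visits 1-7 with that option at both Visits 6 and 7: subset 398 + 73 = 471 mL; non-subset 374 + 73 = 447 mL (451 with the week-1 draw). This needs screening within 3 days of insertion and Visit 7 on Day 53, the first day of its window.
- At 471 mL, 4 mL remain. A fifth repeat sample of 1.0 mL passes the limit.

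**Waste.** The protocol fixes no volume per draw, so this is an assumption, applied to glucose draws only. Subset Visits 1-6 have 3 × 89 + 67 = 334 glucose draws.

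| Blood wasted per draw (mL) | Subset, Visits 1-6 (mL) |
|---|---|
| 0.1 | 431 |
| 0.2 | 465 |
| 0.3 | 498 |
| 0.5 | 565 |
| 1.0 (the 5.9.1 example) | 398 + 334 = 732 |

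Break-even by Visit 6: (475 − 398)/334 = 0.23 mL per draw for the subset and (475 − 374)/334 = 0.30 mL for other subjects.

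**The case against.** Several defenses have force.

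- **The 8-week limit is the operative control.** Section 5.9.1 binds sites to it and warns about wasting, and every pre-waste total complies. This stands. It does not rescue 8.2.3, which speaks of the study and does not mention 8 weeks.
- **In-clinic testing might mean glucose samples only.** That gives 3 × 89 + 3 × 59 = 444 mL, or 3 × 89 + 3 × 67 = 468 mL, both under 475. The text does not say so, dexamethasone and A1C are also drawn at clinic visits, and the risk conclusion concerns all blood lost.
- **The sentence is true for some subjects.** With no challenges the study total is 6 + 4 + 3 × (65 + 8) + 3 × (51 + 6) = 400 mL. With hyperglycemia challenges only it is 6 + 4 + 3 × (73 + 8) + 3 × 65 = 448 mL. The subset adds 24 mL: 424 and 472. The sentence fails for those who complete the scheduled hypoglycemia challenges.
- **Expected volume may be lower than the budget.** Protocol 11.1.4 expects 22,786 pairs from 66 sensors, about 345 per sensor. Taking pairs as a proxy for draws and adding 52 mL of dexamethasone and A1C gives about 397 mL, or 421 mL for the subset. But unpaired samples are not counted, and 8.2.3 does not claim to describe an average.
- **A qualifier may exist.** SAP Table 1 marks its blood-volume row with a footnote 4 whose text is not in the copy available here.
- **Consequences are limited.** Hematocrit must be in range before each accuracy visit (4.4.5, 4.5.6, 4.6.6).

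In the other direction, a reader might infer that the plan breaches its own 8-week limit, or that sites will draw 732 mL by Visit 6. The documents support neither. The pre-waste worst case is 471 mL, closed-loop sampling is allowed, and the 1.0 mL figure is an illustration, not a prescribed volume.

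**Conclusion.** The contradiction is established without assumptions: 8.2.3 says below about 475 mL over the study, and the protocol's own sum is 504 mL. The correct comparison is 475 mL per 8 weeks.

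The published maximum is also too low. Only 16 mL is omitted unconditionally, giving 520 mL for a subset subject. A reader might take 544 mL as the volume every subset subject gives. It is a conditional ceiling, requiring a first glucose below 180 mg/dL and a challenge run to target at all of Visits 6, 7 and 8.

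Before waste there is no breach of the 8-week limit. The 471 mL case needs a subset subject, screening within 3 days of insertion, Visit 7 on Day 53 and full hypoglycemia challenges at Visits 6 and 7, all together. Whether waste causes a breach depends on technique and on a volume the protocol does not set; the operations manual was not available.

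This should be fixed because a wrong figure supports a stated safety conclusion. The accuracy and safety endpoints are unaffected.

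**What to change.** 1. In 8.2.3, state the true study total and compare the worst 8-week total (471 mL before waste) with 475 mL per 8 weeks.
2. Correct the maximum volumes in the Protocol visit table, 4.6.17, Section 6 and SAP Table 1 to include the Day 3-6 draws and 2-hour hypoglycemia sampling: 73 mL per visit at Visits 6-8 under that option, and 520 mL, up to 544 mL, for a subset subject before waste. Show waste separately by technique.
3. In 5.9.1, state that wasted blood and repeat samples count toward the 475 mL per 8-week limit.

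I would not mandate closed-loop sampling or a small waste cap. Section 5.9.1 notes that the single-stopcock technique carries a lower risk of diluted samples, and the reference glucose is the denominator of MARD. Nor would I set a fixed earliest day for Visit 7, because 4.4.5 lets Visit 3 be rescheduled. With Visit 3 on Day 4 and Visit 7 on Day 58, Visits 3-7 fall within 56 days and total 3 × 97 + 2 × 73 = 437 mL. Even 0.2 mL of waste on 401 glucose draws takes that to 517 mL. Counting actual volume against the limit handles such cases directly.

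The cost is wording, two tables and a larger, less favorable stated blood volume.
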